In addition, treatment with osilodrostat can potentially result in neutropenia, which is considered to be an indirect effect of cortisol reduction, as reported in the literature. During hormonal control, a significant decrease of neutrophil count, which is commonly elevated in patients with Cushing's disease, has been reported demonstrating the effect of glucocorticoids on these blood cells (Masri-Iraqi et al, 2014). This effect has also been observed with osilodrostat in the Cushing's disease trials and has included cases of neutropenia which were associated with mUFC levels that were either below normal or have had a rapid and substantial decline from baseline. In the cases observed, neutropenia has rapidly reversed with discontinuation of osilodrostat, and has also reversed when osilodrostat was continued, typically with decreasing doses.

Potential risks of osilodrostat treatment in study population

Potential risks of treatment with osilodrostat in patients with Cushing's disease include: QT prolongation, adrenal insufficiency, AEs related to the accumulation of precursor molecules, including: increased or decreased blood pressure, hypokalemia or hyperkalemia, hyponatremia, weight gain, edema, and increase in the synthesis of sex steroids (primarily adrenal androgens in women) that may lead to menstrual changes and hirsutism in women and acne in men and women. Corticotroph tumor progression, with or without compressive symptoms, is another potential risk. Skin rash has also been observed.

Mitigation of the potential risks related to osilodrostat treatment include: frequent study visits with careful monitoring for adverse events and toxicities including those that have been observed in previous studies with osilodrostat; vital signs, blood chemistry including urine, serum, and salivary cortisol levels, plasma ACTH, electrolytes, renal and liver function, fasting lipid profiles, HbA1c, sex steroid levels (testosterone, estradiol, adrenal androgens), aldosterone and immediate precursor levels, safety ECGs at the time of C_{max}, pituitary MRI scans, and bone mineral density.

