For cardiovascular and metabolic parameters associated with Cushing's disease (e.g. fasting glucose, HbA1c, fasting lipid profile, SBP, DBP, weight and waist circumference):

For actual and percentage change from baseline to Week 12, Week 36 and Week 48, descriptive summaries will be provided by treatment arm and for overall patients.

For the actual and percentage change from the baseline to the end or the last available measurement of the placebo control period, whichever occurs earlier, in addition to the descriptive summary, the mean difference between two randomized arm and associated 2-sided 95% C.I. will be estimated with adjustment for corresponding baseline parameter value. In addition, shift tables using normal/abnormal categories for BP (SBP, DBP), FPG, HbA1c, fasting lipid profile, weight and waist circumference from baseline at Week 12, 36, and 48 by randomized arms and for overall patients will be assessed. Normal for these parameters is defined as shown in [Appendix 3](#).

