Appendix 3: Normal ranges for cardiovascular risk factors

Parameter	Conventional Units	SI Units	Comment
Systolic blood pressure (SBP)	90-139 mmHg	90-139 mmHg	Conventional and SI units are the same
Diastolic blood pressure (DBP)	60-90 mmHg	60-90 mmHg	Conventional and SI units are the same
Fasting plasma glucose (FPG)	70-115 mg/dL 70-125 mg/dL	3.9-6.4 mmol/L 3.9-6.9 mmol/L	Age 13-49 years Age ≥ 50 years
HbA1c	< 6.5 %	< 6.5 %	Percent of total hemoglobin
Total cholesterol	< 170 mg/dL < 200 mg/dL	0.00-4.35 mmol/L 0.00-5.15 mmol/L	Age 3-19 years Age ≥ 20 years
HDL cholesterol	> 34 mg/dL	> 0.89 mmol/L	All adult ages
LDL cholesterol	0-110 mg/dL 0-130 mg/dL	0.00-2.85 mmol/L 0.00-3.35 mmol/L	Age 3-19 years Age ≥ 20 years
Triglycerides	< 200 mg/dL	2.24 mmol/L	All adult ages SI: Age 13-64 years SI: Age ≥ 65 years

Source: [Chobanian A, et al JNC 7 \(2003\)](#). FPG, HbA1c : [ADA Diabetes Standards 2015](#) .
Lipids: Central Laboratory Reference Ranges as of writing of original version of this protocol (consult Laboratory Manual for most current information).

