For the actual value and change from the baseline to Week 12 or the last available measurement of the placebo control period, whichever occurs earlier, in addition to the descriptive summary, the mean difference between two randomized arms and associated 2-sided 95% C.I. will be estimated with adjustment for corresponding baseline parameter value. In addition, shift tables using normal/abnormal categories for BP (SBP, DBP), FPG, HbA1c, fasting lipid profile, weight and waist circumference from baseline to Week 12, 36, and 48 by randomized arms and for overall patients during the open-label period will be assessed. Normal for these parameters is shown in protocol Appendix 4. FAS will be used for this analysis.

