2.8.3 Laboratory data

Laboratory data summaries will include all assessments available for the lab parameter collected no later than 30 days or safety follow-up whichever is later after the last study treatment administration date using data from all sources. All laboratory assessments will be listed and those collected later than 30 days after the last study treatment date will be flagged in the listings.

Grading of laboratory values will be assigned programmatically as per NCI Common Terminology Criteria for Adverse Events (CTCAE) version 4.03. The calculation of CTCAE grades will be based on the observed laboratory values only, clinical assessments will not be taken into account.

CTCAE Grade 0 will be assigned for all non-missing values not graded as 1 or higher. Grade 5 will not be used. For laboratory tests that are graded for both low and high values, summaries will be done separately and labeled by direction, e.g., sodium will be summarized as hyponatremia and hypernatremia.

For laboratory tests where grades are not defined by CTCAE, results will be categorized as low/normal/high based on laboratory normal ranges.

For laboratory tests where grades are defined by CTCAE

- Summary table for AEs of grades 3 or 4
- Worst post-baseline CTCAE grade (regardless of the baseline status). Each patient will be counted only once for the worst grade observed post-baseline.
- Shift tables using CTCAE grades to compare baseline to the worst on-treatment value

For laboratory tests where grades are not defined by CTCAE ,

- Shift tables using the low/normal/high/ (low and high) classification to compare baseline to the worst on-treatment value

In addition, the following laboratory results will be summarized.

- Selected laboratory data will also be displayed by presenting summary statistics of change from baseline value
- Patients meeting categorical liver function test criteria, including Hy's Law criteria for liver injury (ALT or AST > 3 x ULN and TBIL \geq 2 x ULN and ALP < 2 x ULN), e-dish plot may be provided as well

The following listings will be produced for the laboratory data:

- Listing of all laboratory data with values flagged to show the corresponding CTC grades the classifications relative to the laboratory reference ranges
- Listing of notable laboratory abnormalities (i.e. CTC grade 3 or 4 laboratory toxicities).

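### For SBP, DBP and fasting glucose, the normal/abnormal shift tables pool values below and above range and so lose direction; weight and waist circumference have no range at all

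*SAP*

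**What the plan says.** Core SAP 2.7.5 calls for "shift tables using normal/abnormal categories for BP (SBP, DBP), FPG, HbA1c, fasting lipid profile, weight and waist circumference", from baseline to Weeks 12, 36 and 48, by randomised arm and for all patients in the open-label period. Protocol 10.5.2.5 has the same rule: "shift tables using normal/abnormal categories for BP (SBP, DBP), FPG, HbA1c, fasting lipid profile, weight and waist circumference from baseline". Both documents send the reader to a protocol appendix for what counts as normal. In the current protocol this is "Appendix 3: Normal ranges for cardiovascular risk factors".

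That appendix gives SBP 90-139 mmHg, DBP 60-90 mmHg, and FPG "70-115 mg/dL 70-125 mg/dL" (ages 13-49, then 50 and over). The other limits are one-sided: HbA1c below 6.5%; total cholesterol "< 170 mg/dL < 200 mg/dL" by age group; triglycerides below 200 mg/dL; LDL from 0 to 110 or 130 mg/dL by age group; HDL above 34 mg/dL. There is no row for weight or waist circumference.

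The shift table is named in the secondary objective itself (Protocol Table 3-1, Core SAP Table 1-1). Elsewhere the SAP keeps direction. For laboratory tests without CTCAE grades, section 2.8.3 specifies "Shift tables using the low/normal/high/ (low and high) classification to compare baseline to the worst on-treatment value".

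**The concern.** Neither document says that abnormal means high only. With a two-sided range and two categories, abnormal covers two opposite clinical states. The table then cannot separate persistent hypertension from hypertension that has overshot, or a new low value from a new high one.

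This matters more for this drug than for one that moves blood pressure in a single direction, because Protocol 2.6 lists "increased or decreased blood pressure, hypokalemia or hyperkalemia" among the potential risks. A reader of the shift tables would naturally take a move from normal to abnormal as deterioration in a Cushing's comorbidity, and abnormal at both visits as no change. For SBP, DBP and FPG neither reading is safe.

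Weight and waist have a separate gap. They are listed for classification, but no limit is given, so someone would have to choose one later without documentation.

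**Working it through.** The plan states no figure to reproduce here. The check is to classify values under the planned rule and under a directional rule, and compare the cells.

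**1. What the collapse does.** Low/normal/high at two visits gives 3 × 3 = 9 cells; normal/abnormal gives 2 × 2 = 4. For a two-sided range the nine map to four as follows:
- *abnormal to abnormal* absorbs 4 cells (high-high, high-low, low-high, low-low);
- *normal to abnormal* absorbs 2 (normal-low, normal-high);
- *abnormal to normal* absorbs 2 (low-normal, high-normal);
- *normal to normal* is 1.

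Total 4 + 2 + 2 + 1 = 9.

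**2. Worked pairs.** The limits are from Protocol Appendix 3 (FPG under age 50, lipids at age 20 and over). The patient values are invented for illustration.

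| Parameter | Baseline, later | Planned rule | Low/normal/high |
|---|---|---|---|
| SBP | 165, 85 | abnormal to abnormal | high to low |
| SBP | 120, 85 | normal to abnormal | normal to low |
| SBP | 120, 150 | normal to abnormal | normal to high |
| DBP | 98, 55 | abnormal to abnormal | high to low |
| DBP | 75, 55 | normal to abnormal | normal to low |
| FPG (mg/dL) | 140, 65 | abnormal to abnormal | high to low |
| FPG (mg/dL) | 95, 65 | normal to abnormal | normal to low |
| HbA1c (%) | 7.5, 5.0 | abnormal to normal | high to normal |
| Total cholesterol | 240, 120 | abnormal to normal | high to normal |
| LDL | 160, 60 | abnormal to normal | high to normal |
| Triglycerides | 250, 60 | abnormal to normal | high to normal |
| HDL | 50, 30 | normal to abnormal | normal to low |

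The second and third rows move in opposite directions and fall in the same planned cell. In the last five rows the range has only one abnormal side, so nothing is lost.

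**3. Scope.** Eight parameters have a range: SBP, DBP, FPG, HbA1c, total cholesterol, HDL, LDL and triglycerides. Three of the eight are two-sided.

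**4. Weight and waist.** No range exists. The notable-weight criteria in Core SAP 2.8.4.2 (a gain of at least 10% or a loss of at least 5%) are defined relative to baseline. They give no baseline category and cannot stand in for one.

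**5. Illustrative tail areas.** All means and SDs below are assumed, with normal distributions; none comes from the documents. Low share = P(low) / [P(low) + P(high)].
- DBP, mean 80, SD 10: P(<60) = 0.0228, P(>90) = 0.1587; low share 0.0228/0.1815 = 13%.
- DBP, mean 78, SD 9: 0.0228 and 0.0912; low share 20%.
- FPG against 70-115, mean 95, SD 15: 0.0478 and 0.0912; low share 34%.
- FPG against 70-115, mean 90, SD 12: 0.0478 and 0.0186; low share 72%, but of only 6.6% abnormal in total.

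These are shares at a single visit. They do not give the joint probability of being high at baseline and low later, and SBP was not computed.

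**The case against.** The strongest reply is that little is lost overall. Core SAP 2.7.5 also summarises actual values and change at Weeks 12, 36 and 48, and the SAP's default continuous summary includes the minimum and maximum. For the placebo-controlled period it adds a baseline-adjusted difference between arms with a 95% CI. Safety vital signs have separate high and low criteria (2.8.4.2), and laboratory tests are summarised by direction (2.8.3). This stands: a reader might infer that the plan hides over-treatment, and it does not.

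Those outputs still do not replace a directional table. Continuous summaries do not count patients who moved between categories. The safety shift tables use the worst on-treatment value, not the scheduled weeks, and their limits differ: notable low DBP needs 50 mmHg or less with a fall of at least 15 mmHg, so 51-59 mmHg is below the Appendix 3 range but not notable.

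Two further inferences are tempting and should not be drawn.
- *That the distortion is unequal by arm.* Protocol 2.6 lists blood pressure changes in both directions, Protocol 1.2.1.2.3 reports no clinically relevant change in mean vital signs in earlier experience, and after Week 12 all patients receive osilodrostat. A contrast with placebo exists only at Week 12, and no figure supports an imbalance.
- *That the SAP's appendix reference is an error.* "Normal for these parameters is shown in protocol Appendix 4" was written in April 2019; Amendment 2 of December 2019 later deleted an appendix. It is a version difference.

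It is also fair that a move from SBP 165 to 85 is not normalisation, so keeping it out of *abnormal to normal* is right. The fault is that it is indistinguishable from persistent hypertension. Section 2.7.5 itself labels no cell as benefit or worsening.

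**Conclusion.** The point holds for SBP, DBP and FPG only. Applied as written, the two-category rule loses direction in the visit-specific shift tables for these three parameters, and the tables for weight and waist circumference are unspecified. HbA1c and the lipids are unaffected, as are the primary and key secondary tests.

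The logical result rests only on the Appendix 3 limits and on reading abnormal as outside the range in either direction, which is how the text stands. How many patients would be misplaced is unknown. The tail areas show that low values could be a minor or a major part of the abnormal category depending on what is assumed; they are not estimates. Under the first DBP assumption, 2.3% of the planned 46 osilodrostat patients is about one patient (0.0228 × 46 = 1.05). This is a modest weakness in descriptive tables, worth correcting because they are named in a stated objective and the correction is nearly free.

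**What to change.** In Core SAP 2.7.5 and Protocol 10.5.2.5, specify low/normal/high categories for SBP, DBP and FPG, in line with the practice in SAP 2.8.3 for ungraded laboratory tests. Keep normal/abnormal for HbA1c and the lipids.

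For weight and waist circumference, choose one of two routes:
- define the categories and add them to the appendix, which leaves the objective as it is; or
- remove both from the shift-table lists everywhere, including the secondary objective and any matching endpoint text (Protocol summary, Protocol Table 3-1 and the SAP objective tables). Deleting them only from the analysis sections would contradict the objective. Their change from baseline is summarised in any case.

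The cost is wording plus one extra row and column in the tables for three parameters. The second route for weight and waist also needs an edit to the objective. No new data, tests or sample size changes are involved.

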2.7.6 Assess the change from baseline in physical features of Cushing's disease

For each of physical features of Cushing's disease: facial rubor, striae, supraclavicular fat pad, dorsal fat pad, proximal muscle wasting (atrophy), central (abdominal) obesity, and ecchymoses (bruises), Likert scores will be measured. The change from baseline at Weeks 12, 36 and 48 will be assessed by shift tables in each of the randomized treatment arms. The change will also be provided for overall patients in open-label period. In addition, the proportions of patients having a favourable shift from baseline to post-baseline time points will be tabulated. FAS will be used for this analysis.

2.7.7 Assess the change from baseline in bone mineral density by DXA scan at Week 48

For bone mineral density measured by DXA scan at the lumbar spine and total hip, descriptive summaries of actual and percentage change from baseline to Week 48 will be provided by randomized treatment arm and for overall patients. FAS will be used for this analysis.

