To assess the change from baseline at Weeks 12, 36, and 48 in physical features of CD.	Mean change from baseline to Week 12, Week 36, and Week 48 in each of the following clinical signs of Cushing's disease, captured by: a semi-quantitative Likert scale for facial rubor, striae, supraclavicular fat pad, dorsal fat pad, proximal muscle wasting (atrophy), central (abdominal) obesity, and ecchymoses (bruises) by randomized treatment arm and overall population.	
To assess the change from baseline in bone mineral density (BMD) by DXA scan at the lumbar spine and total hip at Week 48.	The change from baseline in bone mineral density, and BMD T-score, at the lumbar spine (L1-L4) and total hip at Week 48 by treatment arm and for overall patient population.	
To determine the safety and tolerability of osilodrostat in the study population.	Adverse events and laboratory abnormalities. Assessed events include: AEs of special interest, laboratory evaluation, ECG, Holter recording, and pituitary MRI.	
To assess the change from baseline in Health Related Quality of Life, as measured by the CD-specific QoL questionnaire (CushingQoL); by the Beck Depression Inventory (BDI-II); and by the general health-related QoL instrument EQ-5D-5L, by randomized treatment arm and overall.	Change in standardized score of CushingQoL, Beck Depression Inventory-II, and EQ-5D-5L, from baseline to Week 12 and Week 48, from Week 12 to Week 36, and from Week 36 to Week 48, or the last measurement prior to early discontinuation, whichever occurs earlier.	
To evaluate pharmacokinetic exposure of osilodrostat in the study population.	Plasma concentrations (pre-dose, 1-2 h post-dose) of osilodrostat.	
To assess the change from baseline in serum, salivary and hair cortisol levels	The actual and percentage change from baseline in serum cortisol, late night salivary cortisol, morning salivary cortisol and hair cortisol levels for every visit in the Core and extension phases at which the biomarkers of hypercortisolism are collected, by treatment arms and for all patients.	

Objective	Endpoint	Analysis
		

4 Study design

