7.2.1.2 Physical features of Cushing's disease

The following clinical signs (physical findings) of Cushing's disease will be assessed clinically for severity at time points defined in Table 7-1a, Table 7-1b, Table 7-2 and Table 7-3: facial rubor, hirsutism (female only), striae, supraclavicular and dorsal fat pads, proximal muscle wasting (atrophy), central (abdominal) obesity, and ecchymoses (bruising). These clinical signs are to be rated on a semi-quantitative scale as follows: 0=absent; 1=mild; 2=moderate; and 3=severe.

Physical features of Cushing's disease will also be documented by photography. A total of four photographs will be taken. Two photographs, one frontal and one lateral from the shoulders up will be taken to assess facial plethora (rubor), supraclavicular and dorsal fat pads. Two photographs, frontal and dorsal of the trunk with patient in standing position will be taken to assess striae, proximal muscle wasting (atrophy), central (abdominal) obesity, and ecchymoses (bruising). In order to maintain confidentiality, photographs will not be published without the explicit written consent of the patient. Photographs will be centrally collected and checked for quality by an imaging vendor. The quality checks will be detailed in the vendor manual.

If for cultural reasons, usual lifestyle, or other reasons, photographic assessments cannot be performed, this must be discussed with the sponsor on a case-by-case basis and sponsor approval will be required.

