10.5.2.6 Assess the change from baseline in physical features of Cushing's disease

For each of physical features of Cushing's disease: facial rubor, hirsutism (female only), striae, supraclavicular fat pad, dorsal fat pad, proximal muscle wasting (atrophy), central (abdominal) obesity, and ecchymoses (bruises), Likert scores will be measured. The change from baseline at Weeks 12, 36 and 48 will be assessed using by randomized treatment arm and for overall patients.

10.5.2.7 Assess the change from baseline in bone mineral density by DXA scan at Week 48

For bone mineral density measured by DXA scan at the lumbar spine and total hip, descriptive summaries of actual and percentage change from baseline at Week 48 will be provided by randomized treatment arm and for overall patients.

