In the SAP, clarification is made that efficacy will be summarized by randomized treatment arms during the placebo-control period. The same analysis will be performed by randomized treatment arms and for overall patients during the open-label period.

Safety will be summarized by randomized treatment arms during the placebo-control period. For the overall study period, only safety data associated with osilodrostat treatment will be summarized, which means safety data in placebo-arm collected during placebo-control period will be excluded from the analysis.

5 Appendix

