2.7.6 Assess the change from baseline in physical features of Cushing's disease

For each of physical features of Cushing's disease: facial rubor, striae, supraclavicular fat pad, dorsal fat pad, proximal muscle wasting (atrophy), central (abdominal) obesity, and ecchymoses (bruises), Likert scores will be measured. The change from baseline at scheduled visits will be

summarized. This includes the proportions of patients having a favorable shift from baseline to post-baseline time points. FAS will be used for this analysis.

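### Hirsutism is scored and planned for analysis in the protocol's methods sections, but protocol Table 3-1 and both SAPs leave it out without saying so

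*SAP*

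**What the plan says.** Protocol 7.2.1.2 lists the signs to be rated from absent (0) to severe (3), starting "facial rubor, hirsutism (female only), striae, supraclavicular and dorsal fat pads". Table 7-1a marks physical features as data entered in the clinical database. Protocol 10.5.2.6, in the statistical chapter, names the same eight signs ("facial rubor, hirsutism (female only), striae, supraclavicular fat pad" and so on) and plans the change from baseline at Weeks 12, 36 and 48, by randomised arm and overall.

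The endpoint column of protocol Table 3-1 is different. It defines the endpoint through "a semi-quantitative Likert scale for facial rubor, striae, supraclavicular fat pad" and four further signs, without hirsutism. Table 1-1 of the core SAP (April 2019) and of the final SAP (December 2020) carries the same seven.

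Section 2.7.6 follows the short list in both SAPs: "facial rubor, striae, supraclavicular fat pad" in the core SAP, and in the final SAP "facial rubor, striae, supraclavicular fat pad, dorsal fat" and onwards. The core SAP plans shift tables in each randomised arm and, in addition, the proportion with a favourable shift. The final SAP summarises change from baseline at scheduled visits, including favourable shifts.

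On the drug's effect, protocol 2.6 says that increased sex steroids, chiefly adrenal androgens in women, "may lead to menstrual changes and hirsutism in women and acne in men and women". Table 6-1 lists hirsutism in women among the suspected toxicities of osilodrostat.

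**The concern.** A SAP may narrow what the protocol plans, but it should say that it has done so. Here an analysis planned in the protocol's statistical chapter disappears, and a reader of either SAP has no means of noticing.

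The choice of sign adds weight. Hirsutism is a sign of Cushing's syndrome (protocol 1.1.1) and also a potential effect of the drug, so cortisol control and androgen accumulation could move it in opposite directions. A graded score, taken in everyone at fixed visits and compared with placebo at Week 12, is the planned measurement best suited to show the net result. After Week 12 all patients receive osilodrostat, so the randomised comparison is available only then. Leaving this sign out while reporting the others is open to a charge of selective reporting, even if it happened by accident.

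**Working it through.** No sample size, power or error rate is involved. The check sets the lists side by side, counting the supraclavicular and dorsal fat pads as two signs.

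| Place | Signs listed | Hirsutism |
|---|---|---|
| Protocol 7.2.1.2 (collection) | 8 | yes |
| Protocol 10.5.2.6 (analysis) | 8 | yes |
| Protocol Table 3-1 (endpoint) | 7 | no |
| Core SAP Table 1-1 | 7 | no |
| Core SAP 2.7.6 | 7 | no |
| Final SAP Table 1-1 | 7 | no |
| Final SAP 2.7.6 | 7 | no |

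The other seven are facial rubor, striae, supraclavicular fat pad, dorsal fat pad, proximal muscle wasting, central obesity and ecchymoses. Hirsutism is the only difference in every row.

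**Is the omission disclosed?** Section 4 of the core SAP deals only with presentation by arm and period ("clarification is made that efficacy will be summarized by randomized treatment arms during the placebo-control period"; safety is treated likewise), and Section 4 of the final SAP has the same scope. The core SAP's change history lists several removals, such as the longitudinal models for mUFC and for patient-reported outcomes, but not this one. Section 1.2 of the final SAP says that objectives not reported will be documented in the matching section; its 2.7.6 says nothing about hirsutism.

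**Does another planned output supply the score?** The photographs in protocol 7.2.1.2 are directed at the other seven signs. Adverse event reporting covers part of the ground. Protocol 7.2.2.1 requires significant new or worsening findings to be recorded as adverse events; core SAP 2.8 and 2.8.1 tabulate these by preferred term and, for the placebo-controlled period, by arm. That route depends on the investigator judging the finding significant, does not capture improvement, and gives no shift from a baseline grade. Protocol 8.1.3 names a group of events of special interest for adrenal hormone precursor accumulation, but its list of terms is outside the documents, so whether hirsutism belongs to it cannot be settled here.

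**How much is affected?** One of eight signs, 1/8 = 12.5% of the scored list, in women only. The documents do not give the number of women. Protocol 1.1.1 describes a marked female preponderance in the disease; if women are a majority of the 69 planned patients, at least 35 would contribute.

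**The case against.** The strongest reply is that the SAPs deleted nothing. They reproduce the endpoint as protocol Table 3-1 defines it, and the contradiction lies inside the protocol. That stands as an account of where the conflict starts, and it means that a SAP edit alone would leave the contradiction in place. It does not settle the matter: protocol 10.5.2.6 is the section that plans the analysis, and a SAP facing two lists should choose one openly.

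Three stronger readings that a reader might infer are not supported.

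- *Hirsutism goes unreported.* It does not. Recorded events appear in the preferred-term tables, with a placebo comparison in the core report. The final SAP's safety tables exclude the placebo arm's placebo-controlled period, so that comparison comes from the core report only.
- *The drug is expected to worsen it.* Protocol 2.6 lists it as a potential risk and says only that it may occur. The net direction in treated patients is not stated.
- *The reporting of signs is one-sided.* The shift tables in core SAP 2.7.6 show worsening as well as improvement for the seven listed signs; the favourable-shift proportion is additional.

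Two further points limit the weight. This is a descriptive secondary analysis, away from the primary and key secondary endpoints. And spironolactone, cyproterone acetate and finasteride are permitted for hirsutism (protocol 6.4.1 and Table 6-1), so the scores may partly reflect treatment. That calls for a caveat and does not justify silence.

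**Conclusion.** The point holds as an undisclosed inconsistency with a limited consequence. Followed as written, the SAPs would not produce the scored analysis of hirsutism that protocol 10.5.2.6 plans, including the Week 12 comparison between randomised arms; adverse event tables would be the remaining source on this sign. No efficacy conclusion or error rate changes.

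This rests on two assumptions: that the scores were collected as protocol 7.2.1.2 requires, and that the seven-sign list in 2.7.6 is meant to be exhaustive, as its wording indicates. The documents do not show whether the omission was deliberate.

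**What to change.** Add hirsutism, women only and with women as the denominator, to 2.7.6 and Table 1-1 of the SAPs. Use the same shift tables as for the other signs, at Weeks 12, 36 and 48 by randomised arm, so that worsening and improvement are both visible. The final SAP describes the core results as already reported; if that report is closed, the final SAP can carry the analysis. Its 2.7.6 should then name the Week 12 by-arm table explicitly, because its present text asks only for a summary of change at scheduled visits.

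Align protocol Table 3-1 with protocol 10.5.2.6, so that the endpoint definition and the analysis name the same eight signs. If the exclusion was intended, Section 4 of the SAP should say so and give the reason.

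The cost is one phrase in each list and one extra row per table, from data the protocol already requires, plus a footnote that permitted anti-androgen treatment may affect the scores.
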